We will recruit up to 94 subjects for this study, with the intention of randomizing exactly 64 subjects with OA of the knee for this study. Once we randomize 64 subjects, we will stop recruiting subjects. Subjects will need to meet all of the following inclusion criteria and none of the following exclusion criteria:

Inclusion Criteria:

1. Able to provide informed consent to participate in the study.
2. Subjects between 18-85 years old.
3. Diagnosis of chronic osteoarthritis with pain of either knee as self-reported. *Prior to beginning baseline procedures this must be confirmed by medical records or a letter from the subject's physician, or diagnosis by a study staff licensed physician. This document may either be brought in by the subject or retrieved by study staff after the subject signs a medical release form. If the subject is unable to obtain the medical record, a diagnosis by a study staff licensed physician will be accepted. After consent, if the subject fails to provide the necessary documentation, or if it cannot be retrieved by study staff, the subject will be considered a screen fail.*
4. Existing knee pain of at least 3 on a 0-10 VAS scale on average over the past 6 months.
5. Pain of at least 3 on a 0-10 VAS scale on average over the week prior to the first stimulation session.
6. Pain resistant to common analgesics and medications for chronic pain used as initial pain management such as Tylenol, Aspirin, Ibuprofen, Soma, Parafon Forte DCS, Zanaflex, and Codeine.
7. Having the ability to feel pain as self-reported.

Exclusion Criteria:

1. Pregnancy or trying to become pregnant in the next 6 months.
2. History of alcohol or drug abuse within the past 6 months as self-reported.
3. Contraindications to transcranial brain stimulation or TUS, e.g. implanted brain medical devices or implanted brain metallic devices.
4. Unstable medical conditions (e.g. uncontrolled diabetes, uncompensated cardiac issues, heart failure or chronic obstructive pulmonary disease).
5. Epilepsy.
6. Use of carbamazepine within the past 6 months as self-reported.
7. Suffering from severe depression (with a score of >30 in the Beck Depression Inventory).
8. History of unexplained fainting spells as self-reported.

9. Head injury resulting in more than a momentary loss of consciousness.
10. History of neurosurgery as self-reported.

V. SUBJECT ENROLLMENT

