We anticipate subjects will be primarily recruited through the Spaulding Rehabilitation Hospital/Network (one of the largest rehabilitation centers in the US). SRH provides outpatient services to the Boston area so we anticipate our recruitment procedures will reflect the distribution of races/ethnicities in the surrounding communities. In addition, we will approach colleagues at the other Harvard teaching hospitals, including Brigham and Women’s Hospital (BWH), Massachusetts General Hospital (MGH) and outpatient clinics in the greater Boston area. Furthermore, we plan to advertise this clinical trial in the greater Boston area in a variety of media including on the Internet, via patient registries that are designed to promote research, and in local newspapers. We will also approach senior centers, assisted living facilities and support groups.

Eligible subjects will contact, or give permission to be contacted, by a co-investigator to obtain more information about the study. At the first point of contact (usually a phone call), study co-investigator will administer a phone-screening questionnaire. Once the phone screening process is complete, the information gathered by the co-investigator will be taken to the PI of the study for

further review to confirm eligibility. Data obtained from screening will be stored in a locked filing cabinet in the lab.

Informed consent will be obtained by the study PI and/or a co-investigator (not involved in the patient's care) at Spaulding Rehabilitation Network Research Institute (SRN-RI). The test procedures will be described and the testing equipment will be shown to the subject. Study co-investigators will clearly explain all the procedures and risks of the testing outlined in the consent form. The subject will be given the time needed to consider their decision and will be encouraged to ask questions, both during the initial phone interview and throughout the study. The PI or a co-investigator will answer any questions regarding the study at the time consent is given. Once enrolled, the subject may pause or terminate his/her participation at any time during the study.

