There will be 10 stimulation visits to be completed over 2 consecutive weeks (ideally Monday to Friday of each week). The subject will receive either 20 minutes of active tDCS in conjunction with active TUS, or sham tDCS in conjunction with sham TUS per day for the course of their stimulation visits.

Randomization:

Once eligibility and consent have been approved and completed, after all baseline evaluations and immediately before the first stimulation session, stratified blocked randomization will occur using the randomized list generated by an automatic web-based randomization program (www.randomization.com). A staff member who is not involved in any of the study procedures will be responsible for creating the randomization list and monitoring it during the study. Randomization will be stratified by baseline pain, using the median of Phase I as a cutoff (VAS of 7). Subjects will be randomly assigned to treatment or placebo groups in a 1:1 allocation ratio. We will use permuted blocks of variable sizes (4, 6, and 8) in a random manner to minimize the risk of study staff guessing at the next allocation. Randomization order will be kept in sealed envelopes.

Blinding:

All subjects and investigators will be blinded to the group assignment except for the co-investigators providing stimulation and staff involved in the randomization process (the latter would otherwise not be involved in study procedures). Only the staff involved in the randomization will be authorized to break the blind if there is a clinical need as requested by the PI, clinical care providers, Medical Monitor, or IMC. The patients will remain blinded until they have completed all visits (whether they complete all 16 visits or drop out early), or in the case of an adverse event necessitating un-blinding.

If the subject receives a sham stimulation, he/she may re-enroll into an open label portion of the study, where he/she will receive 10 days of active tDCS/TUS. Un-blinded co-investigators (e.g., who provided stimulation) will coordinate with subjects electing to enter into the open label phase, which will be conducted by the un-blinded study staff. The open-label study will be conducted without informing the blinded assessors of the patient enrollment. In the open label phase, we will complete the VAS assessments on Day 5 and Day 10 of stimulation. This collected data will not be analyzed with the main data collected in the study. This data will be used for exploratory analyses only.

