Before stimulation, the subject will complete a series of assessments:

- Single Leg Standing Balance Test
- Step Test
- Functional Reach Test
- Timed Up and Go Test
- Knee Proprioceptive Test
- Knee Extensor/Flexor Force Test
- Knee Range of Motion (ROM)
- Visual Analog Scale (VAS) for Pain
- Pain/Medication Diary will be given to the subject
- Von-Frey Assessment
- Pain Pressure Test (PPT) with algometer
- Descending Noxious Inhibitory Control (DNIC)
- Visual Analog Mood Scale (VAMS)
- Neurological and Physical Exam

After stimulation subjects will complete the following assessments:

- Visual Analog Scale (VAS) for Pain
- Von-Frey Assessment
- Pain Pressure Test (PPT) with algometer
- Visual Analog Mood Scale (VAMS)
- Descending Noxious Inhibitory Control (DNIC)
- Mini Mental Status Exam (MMSE)
- 4-Choice Reaction Time
- Adverse Events Questionnaire (AEs)

- EEG recording

Visits 4 – 6

Stimulation visits – (Approx Time: ¾ hour)

During the next 3 stimulation sessions – the subject will receive either 20 minutes of active tDCS in conjunction with active TUS, or sham tDCS in conjunction with sham TUS.

Pre-stimulation: immediately before stimulation, subjects will be asked to complete the following:

- Visual Analog Scale (VAS) for pain

After stimulation, the subject will complete a series of assessments:

- Visual Analog Scale (VAS) for Pain
- Visual Analog Mood Scale (VAMS)
- Mini Mental Status Exam (MMSE)
- 4-Choice Reaction Time
- Adverse Events Questionnaire (AEs)

Visit 7

5th Day of stimulation visits – (Approx Time: 2 ¼ hours)

Pre-stimulation: immediately before stimulation, subjects will be asked to complete the following:

- Visual Analog Scale (VAS) for pain

After stimulation subjects will complete the following assessments:

- Single Leg Standing Balance Test
- Step Test
- Functional Reach Test
- Timed Up and Go Test
- Knee Proprioceptive Test
- Knee Extensor/Flexor Force Test
- Knee Range of Motion (ROM)
- Visual Analog Scale (VAS) for Pain
- Pain/Medication Diary
- Von-Frey Assessment
- Pain Pressure Test (PPT) with algometer
- Descending Noxious Inhibitory Control (DNIC)
- Western Ontario and McMaster Universities Osteoarthritis Index (WOMAC)
- Visual Analog Mood Scale (VAMS)
- EEG recording
- Mini Mental Status Exam (MMSE)
- 4-Choice Reaction Time
- Adverse Events Questionnaire (AEs)

- Neurological and Physical Exam

Visits 8 – 11

6-9th Day of Stimulation visits – (Approx Time: ¾ hour)

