All analyses will be conducted according to the principle of intention-to-treat (using regression-based single imputation method). Intention-to-treat (ITT) population will include all randomized subjects. We will also perform an additional sensitivity analysis in which we will use the method of multiple imputation. The primary outcomes will be pain changes as indexed by VAS scores, biomechanical function changes as indexed with the motion analysis suite (i.e., our biomechanical data acquisition and analysis system), and QOL changes. Differences between the groups will be tested using Student's t-test, and additionally we will adjust for important baseline variables and test the time effect in general mixed longitudinal models. This model will be used for the primary and secondary outcomes (dependent variable (one model for each variable): VAS scores, biomechanical function changes as indexed with the motion analysis suite, and QOL changes, and independent variables will be treatment group and time of assessment (we will also adjust for baseline pain levels in this model)). Secondary analyses will be conducted in an exploratory manner (no correction for multiple comparisons). We will also conduct an EEG analysis to correlate EEG data with pain measures. Similar analysis will be conducted for the adverse effects measuring continuous outcome and for the categorical outcomes we will use Fisher's exact test. In both cases, for safety analysis we will use uncorrected p-value to increase the likelihood of detecting detrimental adverse effects.

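### Single regression imputation is the main missing-data method: where tested values are missing, the t-test is over-precise (arm in the model) or its effect is shrunk (arm out)

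*Combined protocol and SAP*

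**What the plan says.** Section VII (Biostatistical Analysis) sets the main method: "All analyses will be conducted according to the principle of intention-to-treat (using regression-based single imputation method". The analysis population is everyone randomized. Multiple imputation comes second: "We will also perform an additional sensitivity analysis in which we will use the method of multiple imputation". The group comparison is by t-test ("Differences between the groups will be tested using Student's t-test"), with mixed longitudinal models in addition, and the primary outcomes are changes in VAS pain, biomechanical function and quality of life. The section does not say which predictors enter either imputation model, whether arm is one of them, whether a random residual is added, or how the standard error allows for imputed values. Nothing in these sentences is redacted.

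Loss of data is foreseen but not quantified. Section VI (Blinding) covers subjects "whether they complete all 16 visits or drop out early". Section V says that "the subject may pause or terminate his/her participation at any time during the study". Section IV adds: "Once we randomize 64 subjects, we will stop recruiting subjects". No replacement of drop-outs is described, and the sample size in Section VII carries no allowance for them.

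**The concern.** Single imputation puts one predicted value where a measurement is missing, and an ordinary t-test then treats it as data. What follows depends on a detail the plan omits.

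- **Arm in the imputation regression:** the filled-in values carry the estimated treatment difference without its uncertainty. The standard error is too small and type I error rises above 5%.
- **Arm left out:** missing subjects in both arms are predicted from the same line. Type I error stays near 5%, but a real effect is biased toward zero.

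Read literally, the sentence also feeds imputed values into the mixed models. Those need none when fitted by likelihood to data missing at random. What is at stake is the error rate or the estimate of the main comparison.

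**Working it through.** **1. The plan's own figure.** Section VII says 32 per group is enough for a standardized effect of 0.9, without alpha or power. Assuming two-sided 5%, power = Φ(0.9·√(32/2) − 1.96) = Φ(1.64) = 95.0%, or 94.3% with the t distribution. The figure is plausible for complete data.

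**2. By hand, no covariate.** Let m be the share missing in each arm, filled with predicted values only.
- Arm in: the sample variance shrinks by (1 − m) while the divisor stays n, so reported SE = true SE × (1 − m). Type I error ≈ 2[1 − Φ(1.96(1 − m))] = 6.3/7.8/11.7/17.0% for m = 5/10/20/30%.
- Arm out: the expected difference is (1 − m) × 0.90 = 0.855/0.81/0.72/0.63.

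**3. Which earlier readings exist before Day 10 (Section VI visit lists).** VAS is taken at baseline and before and after each session. Biomechanical tests are done at Visits 2, 3 and 7. WOMAC is taken at baseline and Visit 7 ("5th Day of stimulation visits"). SF-36 is taken at baseline only.

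**4. Simulation with covariates.** Assumed: 32 per arm, t-test on change scores with SD 1, predicted values only, missing completely at random, 5/10/20/30% missing (about 3/6/13/19 of 64), 40,000 trials per cell.

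| Predictors of the missing value | Arm in: type I error, % | Arm out: estimate of a true 0.90 |
|---|---|---|
| A. Baseline only, r = 0.5 (e.g. SF-36 at Day 10) | 6.0/7.1/10.0/13.9 | 0.85/0.81/0.72/0.62 |
| B. Three earlier readings, all r = 0.5 (biomechanical) | 6.0/6.7/9.2/11.9 | 0.87/0.85/0.79/0.74 |
| B. The same, all r = 0.7 | 5.6/7.0/9.0/12.5 | 0.88/0.85/0.80/0.75 |
| C. Baseline plus one earlier reading, r = 0.8 (possible for VAS) | 5.6/6.1/7.1/8.5 | 0.89/0.88/0.86/0.84 |
| C. The same, r = 0.9 | 5.3/5.5/6.0/6.8 | 0.89/0.89/0.88/0.87 |

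In B the Visit 3 pre-stimulation reading carries no treatment effect and the Day 5 reading carries all of it. In C the earlier reading carries all of it. Earlier readings are never missing in B and C, which favours the plan.

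**5. Cross-checks.**
- Case A, arm in, 20% missing: mean reported SE 0.229 against a true SD of 0.274, ratio 0.836. The two-sided tail beyond 1.96 × 0.836 = 1.64 is about 10%, as in the table.
- A separate run of case A with 3/6/13/19 of 64 missing gave 5.9/6.6/10.1/13.2% and 0.86/0.82/0.71/0.63; hence 13-14% in the last arm-in cell.
- A t-test on the outcome itself (baseline r = 0.5) with 3, 6 and 10 of 32 missing per arm gave 6.9, 9.2 and 14.1% arm in, and 0.82, 0.73 and 0.62 arm out. The hand formula gives 0.90 × 29/32, 26/32 and 22/32 = 0.816, 0.731 and 0.619.
- Adding a random residual is no repair: case A gives 6.1/6.9/9.3/11.9% arm in, with unchanged arm-out shrinkage.
- Letting missingness depend on baseline (case A, and C with r = 0.8) moves arm-in type I error by at most 0.3 points.

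**6. Multiple imputation (20 imputations, Rubin's rules).** In case A with arm in, type I error is 5.0/4.8/4.8/4.8% and the estimate 0.90. With arm out, the estimate is 0.87/0.80/0.71/0.63, so it shrinks just as single imputation does. Power at 0.90:

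| Case | Multiple imputation, arm in, % | Single imputation, arm out, % |
|---|---|---|
| A | 93.3/92.2/88.7/84.2 | 92.8/91.1/85.8/78.5 |
| B, r = 0.5 | 93.3/92.5/89.4/85.3 | 93.4/92.8/90.3/87.4 |
| C, r = 0.8 | 94.0/93.5/92.1/89.9 | 94.3/94.1/93.6/93.2 |

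**The case against.** The strongest reply is that the size is entirely assumed. The documents give no missing rate, and the striking figures sit at 20-30%. Case A is also narrow. No primary time point is stated, SF-36 has post-baseline readings once follow-up visits are analysed, and quality of life is not tied to SF-36 alone. WOMAC has a Day 5 reading and was not simulated. VAS has many readings. The planned multiple imputation would expose a discrepancy, and Section II calls the therapeutic aim preliminary. All of this stands as a limit on size. It does not change the direction, and a sensitivity analysis does not correct the main result.

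Two stronger readings are tempting, and the documents support neither.

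- A reader might infer that the main result is wrong whichever imputation model is used, whenever a tested value is missing. With a strong earlier reading and arm out, type I error stays near 5% and a true 0.90 is estimated as 0.87-0.89. That is a slight bias, and the VAS schedule makes such a reading possible.
- A reader might infer that the planned multiple imputation already avoids both faults, so that exchanging the two labels is enough. Section VII gives no model for it either, and with arm out it shrinks the effect equally.

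**Conclusion.** The point holds in a conditional form and should be fixed. As written, when tested values are missing the main t-test has either an inflated type I error (arm in) or an effect biased toward zero (arm out), and the plan does not say which. The direction follows from the method. The size rests on assumed missing rates, correlations and time point.

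- Nil with complete data, and small at 5% missing or less.
- At 20% missing, arm-in type I error runs from 6.0% (earlier reading with r = 0.9) to about 10% (baseline only), and the arm-out estimate of 0.90 from 0.88 down to 0.72.
- Multiple imputation avoids both faults only with arm in its model and data missing at random.

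The documents do not show that heavy loss is expected. They show only that drop-out is foreseen and not replaced.

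**What to change.** In Section VII:

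1. Make multiple imputation with Rubin's rules the main missing-data method for the t-tests.
2. State its model: treatment arm, the randomization stratum (Section VI: "Randomization will be stratified by baseline pain, using the median of Phase I as a cutoff (VAS of 7"), and the baseline and earlier readings of the outcome concerned.
3. Fit the planned mixed longitudinal models by likelihood to the observed data, without prior single imputation.
4. Drop single imputation, or keep it only as a sensitivity analysis.

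The t-test itself stays; whether the mixed model should replace it is a separate question.

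The cost is SAP wording, since both imputation methods are already named. Intervals widen against arm-in single imputation in proportion to the missing data: at 10% missing by about 10% (case A), 8% (case B, r = 0.5) and 4% (case C, r = 0.8). Where good earlier readings exist, power is somewhat below arm-out single imputation: at 30% missing, 85.3% against 87.4% in case B (r = 0.5) and 89.9% against 93.2% in case C (r = 0.8). With complete data there is no cost.

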For planning sample size calculation for this study, we utilized the OARSI recommendations for the management of knee OA. In this recommendation [84], a panel of experts reviewed evidence for the most commonly used pharmacological and non-pharmacological interventions for OA pain, giving effect sizes for all these interventions. Examples of non-pharmacological interventions are: education, physical therapy, aerobic exercise, knee brace, footwear, thermal modalities, TENS and acupuncture. Examples of pharmacological treatments are: acetaminophen, NSAIDs, injections with corticosteroids and treatment with glucosamine. In this review, effect sizes vary from 0.06 to 0.72. In fact the largest effect size was shown with injection of corticosteroids. Based on these effect sizes and the effect size we found in our pilot data (1.4), we set the effect size for our sample size calculation considering a effect size smaller or equal than our pilot data and larger than the

larger effect size from this meta-analysis (0.72) [84]. For this particular protocol, we plan a sample size of 64 participants. We considered the same sample per group as four times the subjects in Phase 1: 32 subjects per group. This will be enough to detect a difference in effect size of 0.9 and thus an effect size that is superior than other treatments used in OA according to a large guideline on OA management [84], though we expect a larger effect size for pain. However it is important to be able to detect significance with smaller effect sizes in the Phase 2 work, as some of the neurophysiological outcomes require additional power. Note that the main aim here would still be the comparison of active ESSstim vs. sham ESSstim.

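### The only missing-data sensitivity analysis, multiple imputation, shares the main method's missing-at-random assumption, so agreement between the two would not show robustness to outcome-related dropout

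*Combined protocol and SAP*

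**What the plan says.** Section VII sets the main approach: "All analyses will be conducted according to the principle of intention-to-treat (using regression-based single imputation method"). It adds that the "Intention-to-treat (ITT) population will include all randomized subjects", so the outcome of every subject who leaves has to be filled in. The one further step on missing data is "We will also perform an additional sensitivity analysis in which we will use the method of multiple imputation".

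The section does not give the imputation predictors, the missing-data assumption, or any shifted, reference-based or tipping-point analysis. VAS pain change is the first primary outcome named ("The primary outcomes will be pain changes as indexed by VAS scores"). A mixed longitudinal model is also planned, for covariate adjustment and the time effect. Fitted to observed data, that model relies on missing at random too.

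Three other places bear on dropout:
- Section V (Subject Enrollment) lets subjects stop whenever they wish.
- Section VI (Study Procedures), under Blinding, foresees early dropout. It also says that a subject who received sham "he/she may re-enroll into an open label portion of the study, where he/she will receive 10 days of active tDCS/TUS".
- The visit lists in section VI record VAS before and after each of the 10 stimulation sessions and at the four follow-up visits.

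**The concern.** A sensitivity analysis is useful when it varies the assumption in doubt. Here the doubtful assumption is that a subject who leaves would have scored like a subject who stayed and had the same recorded values. Regression imputation and standard multiple imputation both make it. If dropout depends on pain that was never recorded, both are biased together, and their agreement could be read as robustness when it is built in.

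The study has 32 subjects per arm, so three to six leavers per arm can matter. The bias could run either way, and neither planned analysis would reveal it.

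**Working it through.** **1. The plan's own figure.** The plan takes 32 per arm as "This will be enough to detect a difference in effect size of 0.9". It states no alpha, sidedness or power. Assuming two-sided 0.05, power = Φ(0.9 × √(32/2) − 1.96) = Φ(1.64) = 94.9% (94.3% by the t-test). The figure is plausible, and the point below does not depend on it. It serves as a yardstick for the size of a bias.

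**2. Do the two imputations differ?** Single imputation fills a gap with the regression prediction. Multiple imputation draws around that same prediction and averages, so with the same predictors the estimates should coincide. Simulation: 2,000 trials per setting, 32 per arm, no true effect. Predictors were arm and a baseline correlated 0.5 with the outcome, with 20 imputations. False-positive rates are two-sided at 5%. Informative dropout means that poor responders in the active arm leave preferentially and sham subjects leave at random.

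| Dropout per arm (assumed) | Random dropout, false positives: single / multiple | Informative, bias in SD: single / multiple | Informative, false positives: single / multiple |
|---|---|---|---|
| 10% | 7.3% / 4.8% | 0.115 / 0.115 | 10.6% / 8.5% |
| 20% | 10.1% / 5.1% | 0.210 / 0.210 | 22.4% / 13.4% |
| 30% | 14.8% / 5.0% | 0.361 / 0.361 | 47.7% / 28.2% |

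Multiple imputation repairs the variance and does not move the estimate (agreement within 0.001 in every setting). With a true effect of 0.9 and informative dropout, both methods gave about 1.02, 1.12 and 1.25.

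**3. Size and direction.** Let the worst k of 32 leave one arm, at random in the other, and let the imputation predictors explain a share R² of the outcome. The bias is then approximately λ(1 − R²), with λ = φ(z)/(1 − k/32) and z the normal quantile at k/32.
- k = 3 (about 10%): λ = 0.1674/0.9063 = 0.185. With baseline correlation 0.45, bias = 0.185 × (1 − 0.2025) = 0.15.
- k = 6 (about 20%): λ = 0.2692/0.8125 = 0.331; bias = 0.331 × 0.7975 = 0.26.

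Simulation at the same correlation, no true effect, against a nominal 2.5% for falsely declaring active better:

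| Who leaves | 10% missing | 20% missing |
|---|---|---|
| Worst active, random sham | +0.14 SD; 10% | +0.26 SD; 20% |
| Worst sham, random active | −0.15 SD; below 1% | −0.27 SD; below 1% |
| Worst in both arms equally | about 0; 3–6% | about 0; 3–6% |

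Against the design effect of 0.9, the first row is 0.14/0.9 = 16% and 0.26/0.9 = 29%.

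**4. Using interim VAS.** At k = 6, an interim score correlated 0.6, 0.8 or 0.9 with the outcome gives 0.331 × 0.64 = 0.21, 0.331 × 0.36 = 0.12 and 0.331 × 0.19 = 0.06. Simulation with the interim score added to the imputation gave 0.20, 0.13 and 0.06 SD, and false-active rates of 16%, 8% and 5%. If active subjects leave because of interim pain that was recorded and is in the model, the bias is about zero and the rate about 3%.

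**5. What a shift does.** Worsening the imputed active values by δ moves the estimate by (k/32)δ. For δ = 1.0 SD that is 3/32 = 0.094 and 6/32 = 0.188. This takes the informative biases in step 2 from 0.115 to 0.021 and from 0.210 to 0.022 (simulated: 0.022 for both). Under random dropout the same shift pulls the estimate to −0.082 and −0.194. A shift is therefore a stress test to be reported over a range. A single shift should not be read as a correction.

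**The case against.** Much of the case on the other side stands.

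- **The open-label offer.** A reader might infer that it draws out active non-responders and so favours active. The documents do not support this: the offer is for subjects who received sham. As a pain-related reason to leave, it would more naturally remove poorly responding sham subjects, which biases against active. Subjects are blinded while they decide, so an active subject who suspects sham could leave too, but nothing in the text makes that the dominant route.
- **Lack of relief applies to both arms.** If it acts equally, the bias is about zero. The 20% false-active rate needs extreme selection in one arm only.
- **Interim VAS is collected.** Poor relief will often be visible in recorded scores, and an imputation that used them would be much less exposed. The plan does not say that it will.
- **A reader might infer that multiple imputation adds nothing, or can never move the estimate.** It restores the error rate under random dropout. Its estimate is fixed only when both methods use the same predictors, which the plan leaves open.
- **Missing at random is inferred.** Multiple imputation can be run otherwise if the plan says so. This one does not.
- **Exposure may be small.** No dropout rate is given and the primary time point is not named. If it is the tenth stimulation day, subjects have only about two weeks in which to leave.
- **The stage of the study.** The aim is described as preliminary, and no passage contradicts another.

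What remains is that no planned analysis varies the assumption, so the plan could not detect a problem in either direction.

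**Conclusion.** The point holds as a gap in the sensitivity analysis. It does not show that the trial is biased towards active. With the same predictors, the two imputation analyses give essentially the same estimate, so their agreement is not evidence of robustness to outcome-related dropout.

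Under assumed dropout of 10% to 20% and baseline-only prediction, the possible bias runs from about 0.26 SD towards active to about 0.27 SD against it, and is near zero if selection is equal. Well-correlated interim VAS scores would cut it: at 20% missing, to about 0.13 SD at a correlation of 0.8 and 0.06 SD at 0.9. These sizes rest on assumed dropout, correlations and strength of selection, none of which is in the documents. The structural point does not rest on them. This is a cheap improvement to make before unblinding.

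**What to change.** In section VII:

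1. **State the imputation model.** Name treatment arm, baseline VAS and all recorded interim VAS scores as predictors. There are up to 2 × 10 session readings, plus baseline and four follow-ups, making 25. With 64 subjects that may be too many for an unstructured model, so a longitudinal imputation model or pre-specified summaries of the session scores may be needed.
2. **Add a tipping-point analysis for the primary VAS result.** After multiple imputation, add a shift to the imputed values, varied separately in the active and sham arms. Report the combinations at which the conclusion changes. Multiple imputation of active leavers from the sham arm's distribution is an acceptable alternative.
3. **Report the number and timing of dropouts by arm** beside it, so that readers can judge which shifts are plausible.

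The cost is a short paragraph in the plan and a little more programming. It needs no new data and leaves the primary test as it is. The downside is that the supportive estimate may look less favourable.
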